4.1 Potential Adverse Events

The following anticipated adverse events have been identified as possible complications of percutaneous atrial fibrillation ablation procedures in general as well as with the FARAPULSE Endocardial Multi Ablation System:

- Access site complications (e.g., hematoma, pseudo-aneurysm, laceration, bleeding) potentially requiring surgical intervention
- Air embolism
- Allergic reaction or fever resulting from contact with catheters
- Anemia
- Arrhythmia, potentially requiring cardioversion, defibrillation, or rhythm management device
- Arteriovenous fistulae
- Back pain
- Bed sores
- Bleeding, hematoma, hemorrhage or aneurysm at vascular access sites
- Blood pressure changes including hypotension or hypertension
- Coronary artery or vein injury
- Cardiac tamponade or perforation
- Cardiac arrest or cardiac failure
- Catheter entrapment
- Cardiogenic shock
- Conduction system injury resulting in sinus arrest or heart block, either transient or permanent, potentially requiring pacemaker insertion
- Congestive heart failure
- Death
- Drug allergic reaction or side effects (e.g., from contrast, steroids, analgesics, anesthetics, anticoagulants, sedatives, etc.)
- Embolism due to presence of thrombus or introduction of air
- Esophageal injury, ulcer or fistula
- Hemorrhage
- Hemodynamic compromise
- Hemopericardium
- Hemoperitoneum
- Hemothorax
- Local infection, systemic infection, and/or sepsis
- Muscle contractions due to electric stimulation
- Myocardial infarction / transient ischemia

- Nerve damage
- Organ failure
- Pain
- Perforation (e.g., of diaphragm, liver, lung, and/or vessels).
- Pericardial irritation
- Pericardial effusion
- Pericarditis
- Peritonitis
- Phrenic nerve injury with paralysis of the diaphragm and breathing impairment
- Pneumomediastinum
- Pneumopericardium
- Pneumoperitoneum
- Pneumothorax
- Pulmonary vein injury or stenosis
- Risk of cancer or birth defect/harm to fetus from x-ray exposure
- Skin burns/irritation from x-ray exposure
- Stroke/transient ischemic attack
- Surgical procedure to remove retained catheter
- Thrombosis
- Vessel damage, dissection, or occlusion.

4.2 Potential Risks

As detailed in **Section 1.4, Summary of FARAPULSE Clinical Studies**, the risk profile associated with the FARAPULSE Endocardial Multi Ablation System and the ablation procedure is expected to be consistent with similar devices currently in clinical use for percutaneous cardiac ablation for treatment of persistent atrial fibrillation.

The FARAPULSE Endocardial Multi Ablation System is a Pulsed Electric Field (PEF) ablation system that produces continuous transmural cardiac lesions to treat atrial fibrillation using an ablation procedure that is similar to other commercially available percutaneous ablation catheters. More specifically:

- The device system is used during percutaneous endocardial ablation procedures like other commercially approved catheter systems.
- The device system is composed of similar biocompatible materials.
- The device system is a non-thermal ablation technology with targeted cardiac tissue specific mechanism of ablation.
- The device uses the standard percutaneous techniques for ablation procedures.
- The device utilizes a standard irreversible electroporation generator to deliver energy in the form of ablation dose.

A fundamental difference between the FARAPULSE Endocardial Multi Ablation System and other commercially approved atrial fibrillation ablation systems is that the Pulsed Electric Field or irreversible electroporation energy is delivered through

electrodes embedded in the endocardial ablation catheter for delivery of such energy in the pulmonary veins.

As such, the potential risks are roughly equivalent to those associated with commercially released systems being used for percutaneous cardiac ablation procedures. Currently, the complication rates for commercially available catheters are low and have declined as physicians have continued to learn more about cardiac ablation techniques. Furthermore, FARAPULSE, Inc. has conducted bench and in-vivo testing to ensure safe use of the device during clinical investigation and is in compliance with the applicable requirements of the Medical Device Directive 93/42/EEC.

4.3 Potential Benefits

There are no *guaranteed* benefits from participation in this study. Information gained from the conduct of this study may also be of benefit to other persons with the same medical condition.

A study of up to 40 patients for assessment in this protocol will have the following potential benefits:

- To provide treatment to subjects with PersAF using an investigational device which has demonstrated the ability to isolate pulmonary veins and reduce the subsequent occurrence of symptomatic atrial fibrillation in a small number of patients treated for PAF (see **Section 1.4, Summary of FARAPULSE Clinical Studies**);
- To generate additional data demonstrating that the endocardial creation of electrically isolating lesions via Pulsed Electric Field (PEF) catheter ablation applied using the FARAPULSE Endocardial Multi Ablation System is a safe and potentially effective treatment for drug-resistant, recurrent, symptomatic persistent atrial fibrillation (PersAF);
- To assess the feasibility and safety of the FARAFLEX Ablation Catheter for focal ablation in accordance with its proposed indication for use;
- To assess the protocol elements and design for subsequent use in an expanded multi-center European CE Mark Trial.

5. Statistical Analysis and Reporting

A Statistical Analysis Plan (SAP) will be prepared that governs the collection, analysis and reporting of the data from this investigation. This section summarizes the essential elements of that plan.

5.1 General Statistical Considerations

All statistical analyses will be performed using validated statistical software. Continuous variables will be summarized using standard quantitative statistics: number of available observations, mean, standard deviation, median, quartiles and range (minimum and maximum observed values). The number of missing observations will also be specified.

Categorical variables will be summarized using classical frequency statistics: number of available observations and percentages by categories. Percentages will be calculated on the number of available observations. The number of missing observations will also be specified.

When applicable, bilateral asymptotic or exact confidence intervals for binomial distributions will be calculated at the 95% level.

A full data listing will be prepared. Data will be pooled from all study sites.

All related and resulting reports, documents and data will be produced and maintained in such a way as to ensure their control and the protection of subject privacy as far as is reasonably practicable. Data files and analytic reports will be archived according to requisite regulatory standards.

5.2 Control of Systematic Error and Bias

Subjects are not randomized in this single arm study and therefore masking is not achievable. Error and bias are being controlled by several means, including a comprehensive set of study procedures as defined in the protocol to ensure consistent management and outcome measure assessment. Follow-up Holter monitoring and event monitoring data, and all MRI/CT dimensions of PVs, will be assessed objectively by third parties according to standard clinical protocols. Primary effectiveness and safety outcomes will be reviewed by an independent Clinical Events – Data Monitoring Committee (CEDMC). A complete Study Report will allow scientific and clinical reviewers to independently assess potential error and bias.

Study outcomes will be reviewed and adjudicated by an independent Clinical Events and Data Monitoring Committee (CEDMC) more fully described in **Section 9.10, Clinical Events and Data Monitoring Committee.**

5.3 Sample Size Justification

This investigation is the next phase of ongoing feasibility studies to allow the controlled introduction of a new cardiac ablation catheter (FARAFLEX Endocardial Ablation Catheter). This is a feasibility study with no formal hypothesis testing and therefore no required sample size. Study results will be

presented using descriptive statistics. Results from this study will be used to inform and design additional clinical studies.

Forty (40) subjects at up to four sites will allow the assessment of the modified devices and the initial experience and training of investigators and study staff at a new investigational site.

5.4 Subject Disposition

The disposition of all subjects enrolled in the study will be described in tables and diagrams, including numbers screened, treated and assessed at each scheduled follow-up interval. Subjects who do not complete the study will be enumerated and the reason(s) for their discontinuation will be described.

5.5 Imputation for Missing Data

Imputations for missing data in (e.g., withdrawn subjects, loss to follow-up, missing data) will not be performed. Analyses will be performed with all available data only.

5.6 Populations for Analysis

Enrolled Population: all subjects who provided their informed consent.

Safety Subjects/Intent to Treat Subjects: all enrolled subjects except those who terminate their participation prior to the beginning of the Index Procedure.

Per Protocol Subjects: Intent-to-treat subjects for whom the Index Procedure is finished without interfering investigational device deficiency or malfunction.

Reasons for exclusion from the populations will be given, and a summary of adverse events for these subjects, if any, will be provided.

5.7 Final Clinical Report

A final clinical report including these analyses will be prepared at the conclusion of the study or at such time as the study may be prematurely terminated. Copies of the final report will be provided to the investigator and their EC and to the CA as applicable.

6. Outcome Measures

6.1 Primary Safety Endpoint

The primary safety endpoint for this study is the Composite Safety Endpoint (CSE) defined as the incidence of the following early-onset and late-onset serious adverse events (SAEs) which are device- or procedure-related, as adjudicated by the CEDMC and defined below in **Table 4. Composite Safety Endpoint Definitions**.

Early onset (within 30 days of an Index or Remap Procedure)

- Death
- Myocardial infarction (MI)
- Persistent diaphragmatic paralysis
- Stroke or transient ischemic attack (TIA)
- Peripheral or organ thromboembolism
- Pericarditis
- Cardiac tamponade / perforation
- Vascular access complications requiring intervention
- Heart block

Late onset (any time during follow-up through 12 months)

- Pulmonary vein (PV) stenosis (> 70% diameter reduction from baseline)
- Atrio-esophageal fistula

Table 4. Composite Safety Endpoint Definitions

Adverse Event	Description/Criteria
Death	Death
Myocardial infarction (MI)	Myocardial infarction will be demonstrated by any one of the following: 1) detection of ECG changes indicative of new ischemia (new ST-T wave changes or new LBB) that persist for more than 1 hour. 2) development of new pathological Q waves on an ECG 3) imaging evidence of new loss of viable myocardium or new regional wall motion abnormality
Persistent diaphragmatic paralysis	Diaphragmatic paralysis: Change from baseline diaphragmatic function as demonstrated radiographically by elevation of the diaphragm above the normal range but not due to a pulmonary process such as atelectasis. Permanent: not resolved by completion of study follow-up
Stroke or transient ischemic attack (TIA)	Stroke is an acute symptomatic episode of neurological dysfunction attributed to a vascular cause (ischemia or hemorrhage) in which symptoms last more than 24 hours, or if symptoms last less than 24 hours, a brain imaging study demonstrates infarction. Transient ischemic attack is a new focal neurological deficit with rapid symptom resolution always within 24 hours.

Adverse Event	Description/Criteria
Peripheral or organ thromboembolism	Formation in a blood vessel of a clot (thrombus) that results from the breaking loose of all or part of an existing thrombus, which is then carried by the blood to lodge in/occlude a more distal vascular site.
Pericarditis	Inflammation of the pericardial space that results in an effusion that leads to hemodynamic compromise or required pericardiocentesis, prolongs hospitalization by more than 48 hours, requires hospitalization, or persists for more than 30 days following the ablation procedure.
Cardiac tamponade/perforation	The development of a significant pericardial effusion during or within 30 days of undergoing the index AF ablation procedure. A significant pericardial effusion is one which results in hemodynamic compromised (<80mmHg systolic bp), requires elective or urgent pericardiocentesis, or results in a 1cm or more pericardial effusion as documented by echocardiography.
Vascular access complications requiring intervention	Vascular access complication (e.g. groin hematoma, AV fistula, pseudoaneurysm) requiring intervention (e.g. surgical repair, blood transfusion).
Heart block	Impairment of AV conduction requiring permanent pacing intervention, if resulting from inappropriate ablation application.
Pulmonary vein (PV) stenosis	>70% diameter reduction of pulmonary vein from baseline CT/MRA scan.
Atrio-esophageal fistula	Connection between the atrium and the lumen of the esophagus as evidenced by documentation of esophageal erosion combined with evidence of a fistulous connection to the atrium.

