3.9 Duration of Subject Participation

Subjects will be followed at 30 days, 75 days, 6 months and 12 months with a 90-day Blanking Period for recurrent atrial fibrillation, atrial flutter or atrial tachycardia following the Index Procedure.

Reablation with the study device(s) during the Blanking Period is permitted but does not extend either the Blanking Period or the total follow-up interval.

The enrollment period is estimated to take 9 months and subjects will be followed for up to 12 months for a total duration of approximately 21 months.

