3.11.3 Blanking Period

The Blanking Period consists of Day 0 (the date of Index Procedure) through and including Day 90.

During the Blanking Period, any recurrence of AF will be documented; however, recurrences of AF, AFL or AT during this time will not be considered Therapeutic Failures.

Subjects may undergo one repeat ablation during the Blanking Period without creating a Therapeutic Failure, following the procedure detailed in the preceding sections. This may occur during the Remap Procedure or at another procedure as clinically indicated.

If a second repeat ablation procedure is performed during this time, or any nonstudy device is used for cardiac ablation, the subjects will be considered a Therapeutic Failure but will remain in the study.

Towards the end of the Blanking Period, any AFD treatment will be discontinued unless the Investigator deems the withdrawal of AFD treatment not to be in the best interests of the patient.

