3.12.3 Pre-Discharge

Prior to hospital discharge the following data will be collected:

- Adverse Events
- Data regarding the use, changes in or discontinuation of anticoagulation, rate control and/or antiarrhythmic medications.
- Cardiac rhythm as determined by a 12-lead ECG
- Occurrence, date, indication and outcome of any cardioversion(s)
- At the investigator's discretion: a post-procedural mediastinal gadolinium-enhanced MRI
- Stroke/TIA assessments

- NIHSS score
- A neurologic examination will be performed and recorded if:
 - If the NIHSS score has increased by 2 or more points
 - If there is a clinical suspicion of stroke or TIA

3.12.4 30-Day Visit

Discharged subjects will return for an office visit 30 days (\pm 7 days) post-ablation treatment. (Any subject who continues to be hospitalized 30 days post-ablation will have their 30-Day Visit assessment performed in-hospital). The following data will be collected at the 30-Day Visit:

- Adverse Events
- Symptoms of recurrent arrhythmia
- Data regarding the use, changes in or discontinuation of anticoagulation, rate control and/or antiarrhythmic medications.
- Cardiac rhythm as determined by a 12-lead ECG at the time of the visit
- Cardioversions, ablations or hospital admissions since last visit
- Heart failure status as assessed by NYHA classification at the time of visit

3.12.5 75-Day Visit and Remapping Procedure

Patients undergoing protocol-specified remapping:

Subjects will undergo the protocol-stipulated remapping procedure at 75 ± 15 days post-Index Procedure as defined in **Section 3.11.2, 75-Day Remap Procedure**.

- A 3D electroanatomical remapping procedure will be performed to assess electrical isolation of the pulmonary veins. Any electrical gaps may be closed at the investigator's discretion using study devices, or if necessary, a commercially approved ablation device (which constitutes a Therapeutic Failure).
- For patients who received extra-PV ablation at index, including those receiving ablation of the CTI, the persistence of nonconductivity in targeted tissue will be evaluated with either pacing maneuvers or electroanatomical mapping.

Procedure-specific data will be collected as follows:

- Procedural times
- Lesion set data
- Device deficiencies and malfunctions

All subjects whether undergoing remapping or not:

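### Table 4 confines tamponade to the index procedure, against the Index-or-Remap window of the primary safety endpoint, and a permitted unscheduled reablation has no early-onset window of its own

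*Protocol*

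**What the plan says.** **The window.** Protocol 6.1, the executive summary and SAP 2.4.8.1 all use one anchor for the nine early components: "Early onset (within 30 days of an Index or Remap Procedure". Only pulmonary vein stenosis and atrio-esophageal fistula are followed through 12 months whatever the procedure.

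**The tamponade definition.** Protocol 6.1 says that the events are adjudicated by the CEDMC and defined in Table 4. The Table 4 row for cardiac tamponade/perforation reads: "The development of a significant pericardial effusion during or within 30 days of undergoing the index AF ablation procedure". No other row of Table 4 is limited to the index procedure.

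**The SAP derivation.** In SAP 2.5, tamponade is derived from the index date or the remap date, together with an adjudicated criterion equal to Tamponade/Perforation. The other early components are built in the same way. No third procedure date appears.

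**Repeat ablation.** Protocol 3.9 states: "Reablation with the study device(s) during the Blanking Period is permitted". Protocol 3.11.3 adds: "Subjects may undergo one repeat ablation during the Blanking Period without creating a Therapeutic Failure", and on its timing: "This may occur during the Remap Procedure or at another procedure as clinically indicated". A subject who has a second repeat ablation stays in the study. Remap falls between Day 60 and Day 90 (Protocol 3.12.5: "Subjects will undergo the protocol-stipulated remapping procedure at 75 ± 15 days post-Index Procedure"), and blanking ends at Day 90 ("The Blanking Period consists of Day 0 (the date of Index Procedure) through and including Day 90").

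**The concern.** There are two faults, and both can only lower the primary safety rate.

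The first is a contradiction inside Protocol 6.1. The list includes tamponade after a remap; the definition it points to excludes it. Such an event is plausible. Under Protocol 3.11.2 the remap follows the Index Procedure steps as the investigator judges necessary, and those steps include transseptal access. Reablation is allowed in the same session. The SAP does not resolve the conflict. Its date rule would admit the event, but it also needs the committee to have classified the event as tamponade, and a committee working from Table 4 might not.

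The second is an omission. A blanking-period reablation outside the remap is a third kind of procedure with the investigational device, and nothing opens a 30-day window after it. A complication on the day of that procedure enters the early composite only if the date happens to lie within 30 days of Index or Remap.

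At stake is whether the primary safety endpoint covers every permitted use of the device in a study whose stated aim includes judging the system's safety.

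**Working it through.** The plan has no power calculation or performance goal for this endpoint, so there is no figure of its own to reproduce. The check has three parts.

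**1. Tamponade at remap, source by source.**
- Protocol 6.1 list and SAP 2.4.8.1: included (Index or Remap).
- SAP 2.5 date rule: included (index date or remap date).
- Protocol Table 4: excluded ("during or within 30 days of undergoing the index AF ablation procedure").

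Table 4 is the odd one out, but it is the source to which 6.1 sends the adjudicators.

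**2. What one lost event does.** Inputs: n = 40 (Protocol 3.7 and 5.3); 95% intervals (Protocol 5.1, SAP 2.1.4). The sponsor's earlier 40-patient study reported one tamponade (Protocol 1.3.1). That one was at an index procedure, so it shows only that a single event is a realistic count.
- Counted: 1/40 = 2.5%. Clopper-Pearson 95% CI 0.06% to 13.2%.
- Not counted: 0/40 = 0%. Exact upper limit 1 − 0.025^(1/40) = 8.8%.
- SAP 2.1.4 names Agresti-Coull when the proportion is 0%. With z = 1.96, ñ = 40 + 3.84 = 43.84 and p̃ = 1.92/43.84 = 0.0438. The upper limit is 0.0438 + 1.96 × √(0.0438 × 0.9562/43.84) = 0.0438 + 0.0606 = 0.104, or about 10.4%.

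**3. Day count for an unscheduled reablation.** Let it fall on day d (1 to 90) and the remap on day R (60 to 90, or none). The plan counts early events on days 0–30 and R to R+30. A complication on day d itself is missed when 31 ≤ d ≤ R−1. The whole period d to d+30 is missed when 31 ≤ d ≤ R−31.

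| Remap day | Same-day complication missed for d | No day of d to d+30 covered for d |
|---|---|---|
| 60 | 31–59 (29 days) | none |
| 75 | 31–74 (44 days) | 31–44 (14 days) |
| 90 | 31–89 (59 days) | 31–59 (29 days) |
| No remap | 31–90 (60 days) | 31–90 (60 days) |

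Outside these ranges coverage is partial and accidental:
- d = 10: days 10–30 of 10–40 count, 21/31 = 68%.
- d = 80 with R = 75: days 80–105 of 80–110 count, 26/31 = 84%.

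No unscheduled ablation day has all of d to d+30 covered. The last day on which any early event can count is R+30, so Day 90, 105 or 120 for R = 60, 75 or 90. A study-device ablation later than that is wholly outside.

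**The case against.** Four stronger readings are tempting, and the documents do not support them.

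- *Every early complication of an unscheduled reablation is lost.* It is not. Events dated within 30 days of Index or Remap count, and with a Day 60 remap no blanking-period ablation day has zero coverage. Stenosis and fistula count through 12 months.
- *The missed events disappear from reporting.* They do not. Protocol 6.2 includes device- or procedure-related SAEs with no procedure window, and the SAP 2.5 derivation has none either. Stroke and TIA are counted at any time from the index date. All SAEs are tabulated, and the CEDMC adjudicates all adverse events. The loss is from the primary composite only.
- *The plan permits study-device ablation after blanking, so a Day 150 complication is an omitted permitted use.* Express permission covers the Blanking Period. Protocol 6.4 scores a later study-device ablation as a failure of Therapeutic Success, which is not permission. If one happens more than 30 days after remap, its early complications are still outside the window.
- *The step from 1/40 to 0/40 measures the unscheduled-reablation gap.* It illustrates the Table 4 conflict only.

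It can also be said that the SAP, as printed, would catch a Day 45 event. SAP 2.5 writes the condition as 30 ≤ (event date − procedure date), which selects events on or after day 30. That is an evident slip against SAP 2.4.8.1. It would also drop events in the first 29 days after the index procedure, so it is no safeguard.

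Finally, the study is descriptive and tests no hypothesis, so one event reverses no formal decision. That stands, and it limits the weight of the point. It does not remove the contradiction.

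**Conclusion.** The definition is wrong as written and should be corrected.

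The Table 4 conflict is certain on the text. Its effect depends on whether a tamponade occurs at remap and whether the committee follows the row literally. If both happen once among 40 subjects, the estimate falls by 2.5 points to zero, and the upper 95% limit falls from 13.2% to 8.8% (exact) or about 10.4% (Agresti-Coull).

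The missing window for unscheduled study-device reablation is also certain. Its core is Day 31 to the remap, or everything after Day 30 without a remap. Protocol 3.12.5 foresees subjects who decline the remap. The total effect on the rate cannot be computed, because the documents give no expected number of such procedures and no complication rate for them. The direction is known: each subject left out lowers the composite by 2.5 points of 40.

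**What to change.** 1. In the executive summary, Protocol 6.1 and SAP 2.4.8.1, define early onset as within 30 days of any study ablation or remap procedure: Index, Remap, or an unscheduled ablation with the study device.
2. Reword the Table 4 tamponade row to that same window, and give the CEDMC the aligned definition.
3. In SAP 2.5, add the unscheduled-ablation date to each early-component derivation and to the 7-day versions, which use the same two dates. In the same edit, correct the inequality so that it selects events from 0 to 30 days (0 to 7 days) after a procedure. Align the row labels in SAP Tables 8 and 12.

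The cost is small: a few sentences and one more date in the program. Ablations since the last visit are already collected at the 30-day visit and every later one (Protocol 3.12.4 to 3.12.8), and the CRFs record the devices used in each case (Protocol 2.5). The site record must give the date and the device for each such ablation. The downside is that the composite rate may rise slightly.
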